#### Embryofetal Toxicity:

Based on its mechanism of action, pembrolizumab can cause fetal harm when administered to a pregnant woman. Animal models link the PD-1/PD-L1 signaling pathway with maintenance of pregnancy through induction of maternal immune tolerance to fetal tissue. If this drug is used during pregnancy, or if the patient becomes pregnant while taking this drug, apprise the patient of the potential hazard to a fetus. Advise females of reproductive potential to use highly effective contraception during treatment with pembrolizumab and for 4 months after the last dose of pembrolizumab.

**1.2.2 Capecitabine**

Capecitabine is an oral fluoropyrimidine approved for treatment of metastatic breast cancer. Capecitabine is metabolized to 5-FU by an enzymatic process catalyzed by thymidine phosphorylase which has higher activity in tumor tissue compared to normal tissue. A phase II trial by Blum et al demonstrated safety and efficacy of capecitabine in patients with paclitaxel refractory metastatic breast cancer with an overall response rate of 20% and a median duration of response of 8.1 months. Another phase II study of capecitabine monotherapy in patients with both anthracycline and taxane pretreated metastatic breast cancer demonstrated an overall response rate of 28% and median time to progression of 4.9months. Capecitabine has been associated with a favorable risk-benefit profile without having a negative impact on quality of life in patients with metastatic breast cancer. Given the favorable safety profile and relative ease of administration, capecitabine is an ideal agent for consideration of combination therapy for palliative management of metastatic triple negative breast cancer. Currently, there is no randomized control data suggesting survival benefit to combined chemotherapy with capecitabine and the added chemotherapy comes with the risk of additional toxicity.

**1.3 Rationale for the Current Study**

Metastatic TNBC and hormone-refractory MBC are responsible for a disproportionate number of breast cancer deaths. Therefore, there is a significant unmet need to advance the management of MBC. Moreover, there have been fewer advances in the treatment of triple negative breast cancer than have been seen with other subtypes. Interestingly, triple negative breast cancers respond better to chemotherapy, but can become chemotherapy resistant and have a higher recurrence rate compared with other breast cancer subtypes. One mechanism of chemoresistance in TNBC may be the tumors ability to evade the innate immune system. It has been demonstrated that programmed death-1-ligand 1 (PD-L1) expression in cancer cells contributes to immunoresistance. TNBC and basal subtypes of breast cancer are associated with increased expression of PD-L1 and this is associated with poor clinical prognosis. Combining chemotherapy with immunotherapy may allow for a better response to chemotherapy and the innate immune system, leading to improved outcomes. Recent data show safety of pembrolizumab in metastatic TNBC. Capecitabine is an FDA approved drug for metastatic breast cancer, which is effective in TNBC. Combining pembrolizumab with standard of care chemotherapy capecitabine may improve upon survival outcomes for this patient population, whose median survival remains less than one year.

The standard dose used in clinical practice for capecitabine is 1000 mg/m^2. Therefore it would not be necessary to repeat a dose finding phase I study. Furthermore, 2 studies have opened to date (one phase 2, one phase 3) that are evaluating this combination in gastrointestinal (GI) cancers. We do not feel it is necessary to repeat a phase I in only breast cancer patients.

Hence, we are proposing to do a Phase II study of the combination of pembrolizumab and capecitabine for Metastatic Triple Negative Breast Cancer (TNBC) and Hormone refractory breast cancer.

**1.4 Exploratory Studies:**

1. PD-L1 immunohistochemical (IHC) assessment, baseline tissue biopsy of a metastatic will be obtained for PD-L1 immunohistochemical (IHC) assessment. QualTek developed and validated a PD-L1 IHC assay using Merck's proprietary 22C3 antibody, and this will be used for the study. The study site's pathology core will be used to store, process, and ship samples to QualTek. The presence of PD-L1 expression will be correlated with response (PFS, RR) and other clinical-pathologic factors in an attempt to define a subset of patients that may benefit from pembrolizumab.

*Note: The requirement for biopsy (fresh) may be omitted per treating physician's discretion, if the biopsy would cause undue morbidity to the patient and if enough tissue from a prior metastatic lesion (archival biopsy) is not available.*

2. ORR and median-PFS assessment will be done using the irRECIST criteria, which is now applied to immunotherapeutic drugs.

## 2.0 OBJECTIVES

### 2.1 Primary objective(s):

- To evaluate the median progression-free survival (median PFS) for participants receiving pembrolizumab with capecitabine for the treatment of locally advanced or metastatic TNBC and hormone-refractory MBC. This will be assessed by using RECIST 1.1 criteria.

### 2.2 Secondary Objectives:

- To describe the objective response rate (ORR) for participants receiving pembrolizumab with capecitabine for the treatment of locally advanced or metastatic TNBC and hormone-refractory MBC. This will be assessed by using RECIST 1.1 criteria.
- To describe the safety and tolerability of the combination of pembrolizumab and capecitabine for the treatment of locally advanced or metastatic TNBC and hormone-refractory MBC. All adverse events will be assessed by NCI CTCAE 4.03 criteria

### 2.3 Exploratory Objectives

- Analysis of expression of Programmed Cell death 1 Ligand 1 (PD-L1 ) through immunohistochemical (IHC) analysis : A baseline tissue biopsy of a metastatic site will be obtained for PD-L1 immunohistochemical (IHC) assessment, from all patients. An archived specimen may be used (metastatic tissue only) if collected no more than 2 months of registration. Otherwise fresh biopsy of metastatic lesion is mandatory at baseline and should be performed no more than 2 months prior to registration.

*Note: The requirement for biopsy (fresh) may be omitted per treating physician's discretion, if the biopsy would cause undue morbidity to the patient and if enough tissue from a prior metastatic lesion (archival biopsy) is not available.*

*Note: PD-L1 IHC assay from QualTek will be used for the study. Please refer to section 9.1 and laboratory manual for more details.*

- To evaluate ORR and median-PFS using irRECIST:  
To evaluate efficacy endpoint median-Progression Free survival (PFS), assessment will be done up to 1 year after discontinuation of the study drugs. Assessment will be done using irRECIST (see Table 6)

### 3.0 PATIENT ELIGIBILITY

The target population for this study is patients with locally advanced and metastatic TNBC and hormone-refractory MBC. This will be a single-center trial conducted at Northwestern University. Patients will be recruited by the clinical team at Lynn Sage Comprehensive Breast Center of Northwestern University. The investigators may also utilize the services of the Cancer Trial Recruitment Nurse Coordinator as needed to assist with recruitment.

A total of 30 subjects will be needed to obtain 27 evaluable patients on this trial. Approximately 10 potentially eligible patients are seen per month, and it is anticipated that at least 1 per month will be accrued. Potential patients may be referred to the Principal Investigator (PI) at Northwestern University, [name], via the Clinical Research Office at [contact].

Eligibility will be evaluated by the study team according to the following criteria. Eligibility waivers are not permitted. Subjects must meet all of the inclusion and none of the exclusion criteria to be registered to the study. Study treatment may not begin until a subject is registered. Please refer to Section 11 for complete instructions regarding registration procedures.

#### 3.1 Inclusion Criteria

3.1.1 Patients must have histologically-confirmed unresectable, locally advanced or metastatic breast cancer that meets one of the following:

- Triple negative, defined as estrogen receptor (ER) negative, progesterone receptor (PR) negative, human epidermal growth factor receptor 2 (HER2) negative. HER2 negative defined as immunohistochemistry (IHC) 0 or 1+ or fluorescence in situ hybridization (FISH) negative.
- Her2- negative hormone-refractory breast cancer which denotes progression on one or more endocrine therapies (e.g., tamoxifen, aromatase inhibitors, fulvestrant) unless contraindicated.

3.1.2 Patients must be age 18 years or older and may be male or female.

3.1.3 Patients must have an Eastern Cooperative Oncology Group (ECOG) performance status  $\leq 2$ (see appendix 1).

3.1.4 Patients must have a life expectancy of  $\geq 90$  days.

3.1.5 Patients with central nervous system (CNS) involvement may participate if they meet all the following criteria:

- At least 4 weeks from prior therapy completion (including radiation and/or surgery) to starting the study treatment.
- Clinically stable with respect to the CNS tumor at the time of screening

3.1.6 Patients must have baseline laboratory tests within the following parameters within 14 days prior to registration :

System	Laboratory Value
Hematological	
Absolute neutrophil count (ANC)	$\geq 1,500$ /mCL
Platelets	$\geq 100,000$ / mCL
Hemoglobin	$\geq 9$ g/dL or $\geq 5.6$ mmol/L without transfusion or EPO dependency
Renal	

Serum creatinine OR Measured or calculated a creatinine clearance (GFR can also be used in place of creatinine or CrCl)	≤1.5 X upper limit of normal (ULN) OR ≥60 mL/min for subject with creatinine levels > 1.5 X institutional ULN
Hepatic	
Serum total bilirubin	≤ 1.5 X ULN OR Direct bilirubin ≤ ULN for subjects with total bilirubin levels > 1.5 ULN
AST (SGOT) and ALT (SGPT)	≤ 2.5 X ULN
Albumin	>2.5 mg/dL
Coagulation (required only for patients needing biopsy)	
International Normalized Ratio (INR) or Prothrombin Time (PT)	≤1.5 X ULN unless subject is receiving anticoagulant therapy as long as PT or PTT is within therapeutic range of intended use of anticoagulants
Activated Partial Thromboplastin Time (aPTT)	≤1.5 X ULN unless subject is receiving anticoagulant therapy as long as PT or PTT is within therapeutic range of intended use of anticoagulants
a Creatinine clearance should be calculated per institutional standard.	

3.1.7 Females of child-bearing potential (FOCBP) must have a negative serum or urine pregnancy test within 7 days prior to registration. If the urine test is positive or cannot be confirmed as negative, a serum pregnancy test will be required.

*Note: A FOCBP is any woman (regardless of sexual orientation, having undergone a tubal ligation, or remaining celibate by choice) who meets the following criteria:*

- *Has not undergone a hysterectomy or bilateral oophorectomy*
- *Has had menses at any time in the preceding 12 consecutive months (and therefore has not been naturally postmenopausal for > 12 months)*

3.1.8 Female subjects of childbearing potential (FOCBP) must be willing to use an adequate method of contraception as outlined in Appendix 2. Contraception must be used for the course of the study through 120 days after the last dose of study medication.

*Note: Abstinence is acceptable if this is the usual lifestyle and preferred contraception for the subject.*

3.1.9 Male subjects of childbearing potential must agree to use an adequate method of contraception as outlined in Appendix 2. Contraception must be used starting with the first dose of study therapy through 120 days after the last dose of study therapy.

*Note: Male subjects will be considered to be of non-reproductive potential if they have azoospermia (whether due to having had a vasectomy or due to an underlying medical condition)*

*Note: Abstinence is acceptable if this is the usual lifestyle and preferred contraception for the subject.*

3.1.10 Patients must have the ability to understand and the willingness to sign a written informed consent prior to registration on study.

3.1.11 Patients must be willing and able to comply with scheduled visits, treatment plan and laboratory tests.

3.1.12 Patient must be able to swallow and retain oral medication.

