- Patients with controlled Type I diabetes mellitus on a stable dose of insulin regimen for more than a month may be eligible for this study.

- Patients with auto immune disease that does not recur unless patient is exposed to an external trigger (i.e. gluten and celiac disease) may also be eligible.

- 3.2.11 Patients who have evidence of active, noninfectious pneumonitis or have a history of severe pneumonitis that required treatment with steroids are not eligible for this study.  
*(Note: Replacement physiologic dose of steroids (prednisone 10 mg daily or equivalent) are allowed)*
- 3.2.12 Patients who have an uncontrolled intercurrent illness including, but not limited to any of the following, are not eligible:
- Hypertension that is not controlled on medication (defined as  $\geq 140/100$  at rest, average of 3 consecutive readings)
  - Ongoing or active infection requiring systemic treatment
  - Symptomatic congestive heart failure
  - Unstable angina pectoris
  - Cardiac arrhythmia
  - Psychiatric illness/social situations that would limit compliance with study requirements
  - Known positive test for HIV
  - Has known active Hepatitis B (e.g., HBsAg reactive) or Hepatitis C (e.g., HCV RNA [qualitative] is detected).
  - Active tuberculosis
  - Prior allogeneic bone marrow transplantation or solid organ transplant
  - Administration of a live, attenuated vaccine within 4 weeks before starting the study treatment or anticipation that a live attenuated vaccine will be required during the study.
  - Any other illness or condition that the treating investigator feels would interfere with study compliance or would compromise the patient's safety or study endpoints
- 3.2.13 Female patients who are pregnant or nursing (lactating) are not eligible.
- 3.2.14 Patients exhibiting any other condition that would, in the Investigator's judgment, preclude patient's participation in the clinical study due to safety concerns or compliance with clinical study procedures are not eligible for participation. This might include, but is not limited to, infection/inflammation, intestinal obstruction, and/or social/psychological complications.
- 3.2.15 Patients with impaired GI function or GI disease that may significantly alter absorption of oral capecitabine (e.g. ulcerative disease, uncontrolled nausea, vomiting, diarrhea, malabsorption syndrome or small bowel resection) are not eligible for participation.

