 A baseline tissue biopsy of a metastatic site will be obtained for PD-L1 immunohistochemical (IHC) assessment, from all patients. An archived specimen may be used (metastatic tissue only) if collected no more than 2 months prior to registration. Otherwise fresh biopsy of metastatic lesion is mandatory at baseline and should be performed no more than 2 months prior to registration. The requirement for biopsy (fresh) may be omitted per treating physician's discretion, if the biopsy would cause undue morbidity to the patient and if enough tissue from a prior metastatic lesion (archival biopsy) is not available.

PD-L1 IHC assay from QualTek will be used for the study.  
Please refer to section 9.1 and laboratory manual for more details

 Hematology will include white blood cells (WBC) with differential, platelet count, hematocrit, and hemoglobin. To be performed within 14 days before Day1

 Serum Chemistry will include calcium, chloride, creatinine, sodium, potassium, blood urea nitrogen, bicarbonate, glucose, total bilirubin, aspartate aminotransferase (AST), alanine aminotransferase (ALT), alkaline phosphatase (ALP), albumin, and total protein. To be performed within 14 days prior to registration. Patients with liver metastasis will have additional liver function testing done on C1D7 and C1D14, which can be done locally and sent to NU for review.

 This is to be done if the patient is required to have a biopsy (in order to test for bleeding parameters before biopsy). It is to be performed and resulted before the biopsy. (Also refer to footnote 14)

 Serum or urine test for females of child-bearing potential.

 Pembrolizumab will be administered IV at the assigned dose, at Day 1 of every cycle (1cycle =21 days)

 Capecitabine will be self-administered orally by patients at a fixed dose daily on Days 1-14 twice daily, of each cycle.

 A cycle is defined as 21 days (+/- 3 days).

 Patients will be assessed every 3 months up to 2 year after discontinuation of the study drugs for PFS with visits and/or phone calls.

 concomitant medications to be recorded during screening, at the beginning of each cycle and for 30 days after end of treatment

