## Appendix 2: CONTRACEPTION (specifications for Pembrolizumab)

Pembrolizumab may have adverse effects on a fetus in utero. Furthermore, it is not known if pembrolizumab has transient adverse effects on the composition of sperm.

For this trial, male subjects will be considered to be of non-reproductive potential if they have azoospermia (whether due to having had a vasectomy or due to an underlying medical condition).

Female subjects will be considered of non-reproductive potential if they are either:

(1) postmenopausal (defined as at least 12 months with no menses without an alternative medical cause; in women < 45 years of age a high follicle stimulating hormone (FSH) level in the postmenopausal range may be used to confirm a post-menopausal state in women not using hormonal contraception or hormonal replacement therapy. In the absence of 12 months of amenorrhea, a single FSH measurement is insufficient.);

OR

(2) have had a hysterectomy and/or bilateral oophorectomy, bilateral salpingectomy or bilateral tubal ligation/occlusion, at least 6 weeks prior to screening;

OR

(3) has a congenital or acquired condition that prevents childbearing.

Female and male subjects of reproductive potential must agree to avoid becoming pregnant or impregnating a partner, respectively, while receiving study drug and for 120 days after the last dose of study drug by complying with one of the following:

(1) practice abstinence† from heterosexual activity;

OR

(2) use (or have their partner use) acceptable contraception during heterosexual activity.

Acceptable methods of contraception are‡:

Single method (one of the following is acceptable):

- intrauterine device (IUD)
- vasectomy of a female subject's male partner
- contraceptive rod implanted into the skin

Combination method (requires use of two of the following):

- diaphragm with spermicide (cannot be used in conjunction with cervical cap/spermicide)
  - cervical cap with spermicide (nulliparous women only)
  - contraceptive sponge (nulliparous women only)
  - male condom or female condom (cannot be used together)
- hormonal contraceptive: oral contraceptive pill (estrogen/progestin pill or progestin-only pill), contraceptive skin patch, vaginal contraceptive ring, or subcutaneous contraceptive injection

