†Abstinence (relative to heterosexual activity) can be used as the sole method of contraception if it is consistently employed as the subject's preferred and usual lifestyle and if considered acceptable by local regulatory agencies and ERCs/IRBs. Periodic abstinence (e.g., calendar, ovulation, sympto-thermal, post-ovulation methods, etc.) and withdrawal are not acceptable methods of contraception.

‡If a contraceptive method listed above is restricted by local regulations/guidelines, then it does not qualify as an acceptable method of contraception for subjects participating at sites in this country/region.

Subjects should be informed that taking the study medication may involve unknown risks to the fetus (unborn baby) if pregnancy were to occur during the study. In order to participate in the study subjects of childbearing potential must adhere to the contraception requirement (described above) from the day of study medication initiation (or 14 days prior to the initiation of study medication for oral contraception) throughout the study period up to 120 days after the last dose of trial therapy. If there is any question that a subject of childbearing potential will not reliably comply with the requirements for contraception, that subject should not be entered into the study.

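### Section 3.1.7 does not require a baseline pregnancy test in a woman whose amenorrhea of 12 months or more has a potentially reversible medical cause, although Appendix 2 counts her as of reproductive potential

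*Combined protocol and SAP*

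**What the plan says.** Section 3.1.7 limits the pre-registration pregnancy test, due within 7 days before registration, to FOCBP. The note under it gives two conditions, both needed: the woman has had neither a hysterectomy nor removal of both ovaries, and "Has had menses at any time in the preceding 12 consecutive months (and therefore has not been naturally postmenopausal for > 12 months". The note also says that tubal ligation does not take a woman out of the group.

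The table in Section 5.0 shows one pregnancy test, in the screening column. Its footnote 7 reads "Serum or urine test for females of child-bearing potential" and gives no definition of its own.

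Appendix 2 works from the other side. It lists three ways in which a woman can be of non-reproductive potential:

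- item (1): she is "postmenopausal (defined as at least 12 months with no menses without an alternative medical cause";
- item (2): she has had one of the listed operations, which include tubal ligation;
- item (3): she "has a congenital or acquired condition that prevents childbearing".

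Appendix 2 makes contraception a condition of entry: "In order to participate in the study subjects of childbearing potential must adhere to the contraception requirement (described above". The requirement runs "from the day of study medication initiation (or 14 days prior to the initiation of study medication for oral contraception". Section 3.2.13 states "Female patients who are pregnant or nursing (lactating) are not eligible" but names no test.

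**The concern.** The protocol has two rules for deciding whether a woman could conceive, and they disagree about one kind of patient. Appendix 2 asks why menses have stopped; 3.1.7 asks only whether they have. A woman whose periods have been absent for a year or more for a medical reason that may reverse, such as earlier chemotherapy or ovarian suppression, falls between the two. She must use contraception because she might conceive, yet no test is required to show that she has not already done so.

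This matters because the protocol's own safety text states that "pembrolizumab can cause fetal harm when administered to a pregnant woman", and because pregnancy is an exclusion. The rule that decides who is tested before the first dose should not be narrower than the protocol's own account of who may be fertile.

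**Working it through.** The plan gives no figure to reproduce. The check applies both definitions to one case: a woman with uterus, ovaries and tubes intact, and at least 12 months without menses from a potentially reversible medical cause.

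| Rule | Condition | Does she meet it? |
|---|---|---|
| 3.1.7, first bullet | No hysterectomy or removal of both ovaries | Yes |
| 3.1.7, second bullet | Menses within the past 12 months | No |
| **3.1.7 result** | Both bullets needed | **Not a FOCBP** |
| Appendix 2, item (1) | 12 months without menses and no other medical cause | No: there is another medical cause |
| Appendix 2, item (2) | Listed surgery | No |
| Appendix 2, item (3) | Condition that rules out childbearing | No: the cause may reverse |
| **Appendix 2 result** | At least one item needed for exemption | **Of reproductive potential** |

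The next question is whether any other provision requires the test for her.

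- Section 5.0, footnote 7, is limited to women of child-bearing potential. The only note in the protocol that defines that term for testing is the one in 3.1.7.
- Section 3.2.13 excludes a pregnant patient but does not say how pregnancy is to be found.
- The Appendix 2 contraception requirement binds her under that appendix's own definition. It begins on the first day of study medication, or 14 days before for oral contraception. It reduces the chance of a new pregnancy but does not reveal an existing one.

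No other provision requires it. The conflict does not extend to women with any menses in the past 12 months, to women with item (2) surgery, or to women whose condition makes childbearing impossible under item (3).

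Size:

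- Mandated pregnancy tests per affected woman: 1 (screening) becomes 0, a difference of 1.
- Each affected woman as a share of planned accrual: 1/30 = 3.3%.
- Number affected: not estimable. The documents give no age distribution, menopausal status or amenorrhea rate, and the number could be 0.

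**The case against.** The strongest reply is that the second bullet of 3.1.7 states its own purpose. Its parenthesis speaks of natural menopause, which agrees in substance with Appendix 2, so the gap would be loose drafting. That is probably what was meant, and it supports the correction. But the parenthesis is written as something that follows from having had menses. The condition a site applies is menses within 12 months, and an eligibility checklist that follows 3.1.7 would mark the test as not applicable.

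A second reply is that footnote 7 uses nearly the same term as Appendix 2 and could be read through it, which would bring her back into testing. That reading is possible, but it does not displace the explicit definition attached to the testing requirement in 3.1.7.

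Third, 3.1.7 is not looser throughout. It tests women with tubal ligation, whom Appendix 2 item (2) exempts. This is correct, and the remedy should leave it alone.

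Fourth, there are backstops: 3.2.13, the investigator's discretion under 3.2.12 and 3.2.14, the baseline history and full physical examination, and the treating physician's signature on the eligibility checklist. An investigator may also order a test unprompted. These narrow the practical risk, but none of them mandates a test.

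Finally, the size of the group is unknown, and the idea that chemotherapy or ovarian suppression can cause reversible amenorrhea is general clinical knowledge, not something the documents state. That stands as a limit on how much weight the point can carry. The mismatch between the two definitions does not depend on it.

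**Conclusion.** The concern holds. As written, 3.1.7 leaves without a required pregnancy test a woman whom Appendix 2 treats as of reproductive potential, and nothing else in the protocol supplies the test. The conclusion rests on reading the second bullet of 3.1.7 as it stands, and on the view that a potentially reversible cause of amenorrhea is not an item (3) condition.

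The group is narrow. Her contraception obligations are unchanged, and no endpoint or analysis is affected. The correction should still be made: it decides whether a patient whom the protocol regards as possibly fertile must be tested before she receives a drug with a stated fetal risk.

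**What to change.** Amend the second bullet of 3.1.7 so that 12 months without menses removes FOCBP status only when nothing medical other than menopause explains it, in line with Appendix 2 item (1). Keep the item (3) exemption for women whose condition rules out childbearing. Leave the first bullet and the tubal-ligation wording unchanged, so that no woman now tested loses her test. Then have 3.1.8 and footnote 7 of Section 5.0 point to the amended definition.

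The cost is a wording change in the protocol and the eligibility checklist, plus a urine or serum pregnancy test for a few more women.
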